- *This is a “Multi-Site Study that involves more than one site performing ALL aspects of the research procedures as outlined above.” OR “This is a Collaborative Study that involves UT Austin researchers working with external researchers who are engaged in performing the following study activities (list activities).”*
- *For assistance with Multi-Site/Collaborative research, review [UT Guidance: Submitting Studies Relying on UT IRB](#), download HRP-UT932 Request to Rely Assessment Form from the [UTRMS-IRB Library](#) and email [contact].*

This is a single site, randomized, double-blind, placebo-controlled study to evaluate the efficacy of lumateperone as an adjunctive treatment of patients with MDD and a history of early childhood abuse. During the study subjects currently receiving approved dosing regimen of ADT, who experience an inadequate therapeutic response according to MADRS score at Baseline, will be randomized in a 1:1 ratio to Lumateperone 42mg or placebo, and receive treatment for 6 weeks. The primary efficacy analysis will be based on the week 6 assessment of the primary and secondary efficacy endpoints. The overall duration of the study, including Screening and intervention period, will be approximately 9 weeks per subject: a 2-week screening period, 6 weeks of double-blind treatment, and a 1-week safety follow-up visit.

The study design is presented in Figure 1.

Figure 1.

The study will be conducted as follows:

- Screening Period (2 weeks):
- A 2-week Screening Period during which patient eligibility will be assessed. After obtaining written informed consent, diagnostic interviews and physical examinations will be conducted, vital signs and ECGs will be assessed, and blood and urine samples will be collected for laboratory assessments. With the exception of stable, allowed concomitant medications, patients must discontinue prohibited psychotropic drugs during the Screening Period. The following rating scales will be administered.

Clinician Rater: CAPS-5, MADRS, DIAMOND, SCID-5 Borderline Personality module, CGI-S, MGH-ATRQ, CSSRS

PROS, GAD-7, QIDS-SR-16, EQ 5D-5L, CTQ, GASS, PCL-5, NWS, MCI

Once deemed eligible, the subject will also be offered to enroll in the optional EMA wellness app to be completed 3X daily from screening visit to the end of study visit

- Double-blind Treatment Period (DBTP, 6 weeks):

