1.1.1 Dose Selection

Lumateperone capsules are approved in the US by the FDA for the treatment of schizophrenia in adults and for the treatment of depressive episodes associated with bipolar I or II disorder (bipolar depression) in adults, as monotherapy and as adjunctive therapy with lithium or valproate. The recommended dosage regimen is lumateperone 42 mg administered orally once daily. Several studies have shown that lumateperone has a

favorable safety profile, exhibiting a similar tolerance to placebo, with no significant adverse effects reported. The purpose of this study is to determine the efficacy and safety of once daily lumateperone 42 mg as an adjunctive therapy for the treatment of patients with a history of childhood abuse and MDD. Symptoms of depression may or may not improve during participation in this study; half of the patients in this study will receive placebo. However, the information obtained from this study may help to treat people suffering from MDD with history of childhood abuse.

2. Study Population

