2.2 Exclusion Criteria

Patients who meet any of the following exclusion criteria will not be eligible to participate in the study.

Psychiatric Criteria

1. Has a **current primary** DSM-5-TR psychiatric diagnosis other than Major depressive disorder. These include:
 - i. PTSD, OCD, Bipolar Disorder, Schizophrenia, schizoaffective disorder, or other psychotic disorders;
 - ii. Intellectual disability, Dementia or other cognitive disorders;
 - iii. Moderate or severe substance use disorder (excluding for nicotine);
2. In the opinion of the Investigator, the patient has a significant risk for suicidal behavior during the course of his/her participation in the study or
 - i. At Screening (Visit 1), the patient scores “yes” on Items 4 or 5 in the Suicidal Ideation section of the C-SSRS within 6 months prior to Screening; or
 - ii. At Screening (Visit 1), the patient has history of suicidal attempt(s) within 1 year prior to Screening (Visit 1); or
 - iii. At Baseline/randomization (Visit 2), the patient scores “yes” on Items 4 or 5 in the Suicidal Ideation section of the C-SSRS since the Screening Visit; or
 - iv. At Screening (Visit 1) or Baseline (Visit 2), scores ≥ 4 on Item 10 (suicidal thoughts) on the rater administered MADRS; or
 - v. Considered to be an imminent danger to himself/herself or others.

Treatment-related Criteria:

3. MRI contraindications: History of shrapnel or other metal or electronic implants in the body(such as pacemakers, aneurysm clips, ferrous surgical devices, metallic tattoos on the head, etc.). The patient has received electroconvulsive therapy (ECT), vagal nerve stimulation, or repetitive trans-cranial magnetic stimulation within the past 1 year;
4. The patient has known hypersensitivity or intolerance to lumateperone, or to any of the excipients;
5. Treatment with a depot/long-acting injectable antipsychotic within 1 cycle before Screening (Visit 1);
6. The following agents are excluded and must be discontinued at Screening (Visit 1):
 - i. Any moderate or strong cytochrome P450 3A4 inhibitor (CYP3A4), or any CYP3A4 inducer;
 - ii. Central opioid agonists/antagonists, including tramadol;
 - iii. Anticonvulsants, mood stabilizers, antidepressants, stimulants, antipsychotics, and non-benzodiazepine anxiolytics;
 - iv. Dietary supplements and medical foods unless approved by the Sponsor or designee. Daily multivitamin use is permitted;
7. Monoamine oxidase inhibitors within 14 days prior to Baseline/Randomization (Visit 2);

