8. Other drugs with known psychotropic properties or any non-psychotropic drugs with known or potentially significant central nervous system.
9. The patient plans to initiate psychotherapy or make changes to existing psychotherapy during the study (patients who are participating in stable psychotherapy or psychotherapy as a part of their treatment are allowed to enroll);
10. The patient has participated in a previous clinical trial with lumateperone, or has had exposure to any investigational product within 6 months of the baseline visit or participated in > 2 clinical studies

of an investigational product with a central nervous system indication.

Other Medical Criteria:

11. The patient is pregnant or breast-feeding. Female patients of childbearing potential must have a negative serum pregnancy test at Screening (Visit 1). On Day 1 (Baseline/Visit 2), female patients of childbearing potential must have a negative urine pregnancy test prior to study drug administration;
12. The patient has a positive test for alcohol or drugs of abuse (eg, amphetamines, barbiturates, benzodiazepines, cannabinoids, cocaine, methadone, or opioids/opiates) at Screening (Visit 1).
13. The patient has abnormal laboratory values or clinical findings at Screening (Visit 1) including, but not limited to:
 - i. Alanine aminotransferase (ALT) and/or aspartate aminotransferase (AST) $> 2 \times$ the upper limit of normal (ULN);
 - ii. Total bilirubin $> 1.0 \times$ ULN;
 - iii. Hemoglobin $< 8 \text{ g/dL}$ (80 g/L) for females and $< 9 \text{ g/dL}$ (90 g/L) for males;
 - iv. Absolute neutrophil count (ANC) $< 1200 \text{ cells}/\mu\text{L}$ ($1.2 \times 10^9 \text{ cells}/\text{L}$);
 - v. Thyroid-stimulating hormone (TSH) outside of normal reference range AND free T3 or free T4 outside of the reference range. Free T3 and Free T4 will only be evaluated if TSH is outside of reference range;
 - vi. Poorly controlled diabetes as defined by a glycosylated hemoglobin (HbA1c) $> 7.5\%$, despite standard care [$> 58 \text{ mmol/mol}$];
 - vii. Positive test for hepatitis B surface antigen and/or hepatitis B core antibody immunoglobulin M at screening; positive hepatitis C antibody at Screening (Visit 1), with the exception of a patient for whom the reflex HCV RNA test is negative;
 - viii. Any other clinically significant abnormal laboratory result obtained at screening (Visit 1);

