25. Monoamine oxidase inhibitors within 14 days prior to Baseline/Randomization (Visit 2);
26. Other drugs with known psychotropic properties or any non-psychotropic drugs with known or potentially significant central nervous system.
27. The patient plans to initiate psychotherapy or make changes to existing psychotherapy during the study (patients who are participating in stable psychotherapy or psychotherapy as a part of their treatment are allowed to enroll);
28. The patient has participated in a previous clinical trial with lumateperone, or has had exposure to

any investigational product within 6 months of the baseline visit or participated in > 2 clinical studies of an investigational product with a central nervous system indication.

Other Medical Criteria:

29. The patient is pregnant or breast-feeding. Female patients of childbearing potential must have a negative serum pregnancy test at Screening (Visit 1). On Day 1 (Baseline/Visit 2), female patients of childbearing potential must have a negative urine pregnancy test prior to study drug administration;
30. The patient has a positive test for alcohol or drugs of abuse (eg, amphetamines, barbiturates, benzodiazepines, cannabinoids, cocaine, methadone, or opioids/opiates) at Screening (Visit 1).
31. The patient has abnormal laboratory values or clinical findings at Screening (Visit 1) including, but not limited to:
 - i. Alanine aminotransferase (ALT) and/or aspartate aminotransferase (AST) > 2 × the upper limit of normal (ULN);
 - ii. Total bilirubin > 1.0 × ULN;
 - iii. Hemoglobin < 8 g/dL (80 g/L) for females and < 9 g/dL (90 g/L) for males;
 - iv. Absolute neutrophil count (ANC) < 1200 cells/µL (1.2×10^9 cells/L);
 - v. Thyroid-stimulating hormone (TSH) outside of normal reference range AND free T3 or free T4 outside of the reference range. Free T3 and Free T4 will only be evaluated if TSH is outside of reference range;
 - vi. Poorly controlled diabetes as defined by a glycosylated hemoglobin (HbA1c) > 7.5%, despite standard care [> 58 mmol/mol];
 - vii. Positive test for hepatitis B surface antigen and/or hepatitis B core antibody immunoglobulin M at screening; positive hepatitis C antibody at Screening (Visit 1), with the exception of a patient for whom the reflex HCV RNA test is negative;
 - viii. Any other clinically significant abnormal laboratory result obtained at screening (Visit 1);

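### The exclusion for earlier lumateperone use covers trial participation but not prescription, so prior and just-stopped users of a marketed drug can be randomised into a 25-per-arm comparison

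*Protocol*

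**What the plan says.** Protocol section 2.2, exclusion 10, removes a candidate if "The patient has participated in a previous clinical trial with lumateperone, or has had exposure to any investigational product within 6 months", counted back from Visit 2. Section 4.3, item 28, opens the same way: "The patient has participated in a previous clinical trial with lumateperone". The six-month window belongs to investigational products; the lumateperone limb has no time limit.

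Section 1.1.1 states that "Lumateperone capsules are approved in the US by the FDA for the treatment of schizophrenia in adults", and also for bipolar depression. The drug can therefore be obtained outside a trial.

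One other exclusion names the drug, item 4: "The patient has known hypersensitivity or intolerance to lumateperone, or to any of the excipients". Item 6.iii lists "Anticonvulsants, mood stabilizers, antidepressants, stimulants, antipsychotics, and non-benzodiazepine anxiolytics" among agents to be discontinued at Visit 1, with no washout length. The screening description in section 7 agrees: apart from stable, allowed medication, "patients must discontinue prohibited psychotropic drugs during the Screening Period". Table 1 places Screening up to 15 days before Baseline.

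**The concern.** By barring trial exposure without a time limit, the protocol treats earlier lumateperone exposure as disqualifying. The same exposure by prescription is left open, and no reason is given for the difference. A current prescribed user can stop at Visit 1 and be randomised at Visit 2 to the same drug or to placebo.

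Two things are mainly at stake.

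- **Dilution.** Patients who have already had little benefit from lumateperone would be expected to add little to the treatment difference, in a trial whose sample size rationale (item 16) claims only moderate power.
- **Aim 2.** The pre-dose scan serves as a predictor of response and, in section 11.2, as the covariate for the post-treatment scan. In a patient who has just stopped lumateperone it cannot be assumed to be a drug-free scan.

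Two lesser matters follow. A previous user may recognise the drug's effects, and the primary endpoint rests on an interview. Keeping prior users who tolerated the drug while item 4 removes those who did not also tilts the tolerability comparison towards lumateperone.

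**Working it through.** **Step 1: does any other criterion close the gap?**

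| Provision | What it reaches | What it leaves open |
|---|---|---|
| 2.2 item 1 | Current primary bipolar or psychotic disorder, among others | Patients with primary MDD who were prescribed the drug |
| 2.2 item 4 | Prior users who were hypersensitive or intolerant | Prior users who tolerated it, whatever their response |
| 2.2 item 5 | Depot or long-acting injectable antipsychotics | Oral capsules |
| 2.2 item 6.iii | Antipsychotics, to be stopped at Visit 1 | The patient, who may stop and continue in screening |
| 2.2 item 8 | Other psychotropic drugs; the sentence is incomplete and has no look-back period | Past use |
| 2.2 item 10, second limb | Investigational products within six months | Marketed use on the ordinary reading; use over six months ago on any reading |
| 2.2 item 16 and section 3.7 | Investigator judgement and medication review | No stated rule on lumateperone |

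None gives a rule against prescribed exposure.

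**Step 2: who is likely to enter?** Inclusion 4 requires MADRS of at least 22 at Visit 1 and again at Visit 2. A patient still on lumateperone at Visit 1 must reach that score while taking it, so one doing well on the drug fails screening. Those who pass are likely to be poor or partial responders. For patients who stopped before Screening, the documents allow no inference about how they had responded.

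**Step 3: the pre-dose scan.** Section 6 places it in the Screening Period and Table 1 at Baseline. Either way, a patient who stops at Visit 1 is scanned within 15 days of stopping.

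**Step 4: size of the dilution, as an illustration.**

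Inputs:
- 25 per arm, from 50 patients at 1:1 (section 6).
- Two-sided 5% level: assumed.
- True standardised effect d of 0.8 or 0.5: assumed. Item 16 gives no effect size, SD or power figure, so the sample size of 50 cannot be reproduced.
- k complete non-responders in the active arm, meaning patients whose expected difference from placebo is zero: assumed to run from 0 to 3. The documents give no count.

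Formulas: diluted effect d′ = d × (1 − k/25). Power is that of a two-sample t test with 48 degrees of freedom, critical value 2.011 and noncentrality d′ × √(25/2). This is a simplification of the planned MMRM.

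| k | Loss of effect (k/25) | d′ from 0.8 | Power | d′ from 0.5 | Power |
|---|---|---|---|---|---|
| 0 | 0% | 0.800 | 79.1% | 0.500 | 41.0% |
| 1 | 4% | 0.768 | 75.8% | 0.480 | 38.3% |
| 2 | 8% | 0.736 | 72.2% | 0.460 | 35.7% |
| 3 | 12% | 0.704 | 68.4% | 0.440 | 33.2% |

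Under 1:1 allocation, k in the active arm corresponds on average to about 2k such patients among the 50.

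**Step 5: is it adjusted for?** The primary model in section 11.4 contains treatment, visit, their interaction, number of failed prior treatments and baseline score. It has no term for earlier lumateperone use.

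**The case against.** The strongest reply is that the pool is small. Exclusion 1 removes patients whose current primary diagnosis is one of the indications in section 1.1.1, which leaves mainly off-label users who tolerated the drug and still score at least 22. Nothing in the documents suggests how many there are. This stands: the count may be zero, and the power figures are conditional on it.

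There are also partial controls. The investigator reviews recorded medication under section 3.7 and may exclude under item 16. The study drug table in section 3.1 heads lumateperone as an investigational product, so a site might apply the six-month limb to recent prescribed use. These weaken the point for current users, but a discretionary or strained reading is not a rule, and it would not reach older use.

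A reader might infer something stronger: that responders taken off lumateperone and given placebo worsen and so inflate the apparent benefit. The documents do not support that. Inclusion 4 screens out patients doing well on the drug at Visit 1. Change is measured from a Visit 2 baseline that follows discontinuation and is also a covariate. No figure for worsening on withdrawal is given. Randomisation leaves the comparison unbiased in expectation.

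The blinding and tolerability arguments are limited too. Section 1.1.1 describes tolerance similar to placebo, section 3.4 specifies matched appearance, smell and taste, and tolerability is not a confirmatory endpoint. They remain secondary.

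**Conclusion.** The gap in the text is real: one route of prior exposure is barred without time limit, while the other, for a drug the protocol says is approved, is left open. A current user can pass from discontinuation to randomisation in at most 15 days. The supportable consequences are dilution and a pre-dose scan that cannot be taken as drug-free.

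The size rests on an unknown count. With one to three complete non-responders in the active arm, 4% to 12% of the expected difference is lost. With none, nothing is lost to dilution. No figure in the protocol is contradicted, and no bias in favour of lumateperone on the primary endpoint is shown. This is a cheap improvement, between optional and recommended, and no threat to the trial's validity.

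**What to change.** Reword the lumateperone limb of item 10 in section 2.2, and of item 28 in section 4.3, so that it covers previous lumateperone exposure by any route, trial or prescription. Reconcile it with item 6.iii, so that the two items together make clear how someone taking prescribed lumateperone at Screening is handled.

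Check the criterion against the history already collected under section 3.7. That history covers six months for all medication and five years for MDD treatment, so older or non-MDD use would be missed. Add one direct question at Screening about any earlier lumateperone use.

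The cost is one clause in two places, one screening question, and the loss of the few candidates already prescribed the drug. The change protects only patients not yet randomised, so it should be made early.

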2.3 Rescreening

Individuals who sign the ICF to participate in the study but who do not subsequently meet all the requirements as outlined in the inclusion and exclusion criteria and therefore are not randomized (screen failures), may be rescreened once, at the discretion of the Principal investigator with the exception of subjects presenting with alcohol or drug abuse or previously undisclosed psychoactive drugs; subjects excluded because of QTc prolongation or other serious medical conditions at initial screening.

2.4 Study Withdrawal or Removal from the Study

Patients can be prematurely discontinued from the study drug or the study for one of the following reasons:

- Death
- AE
- Lack of efficacy or insufficient therapeutic response
- Lost to follow-up
- Protocol violation
- Study terminated by Investigator
- Withdrawal of consent (by the patient)
- Pregnancy
- Other (such as site closure, administrative reasons, etc)

NOTE: If a patient discontinues due to withdrawal of consent and either a concurrent AE was reported or concurrent lack of efficacy was documented, the study staff will confirm the primary reason for discontinuation and record the primary reason for discontinuation in the subject binder (CRF).

Patients who discontinue from the study and do not return to the study site for final assessments must be requested in writing to return to the site for a final assessment. A copy of the letter, together with the source documentation, will be kept in the Investigator's files. The reason for premature discontinuation from the study will be recorded in the subject study binder.

3. Treatment

3.1 Study Drug Administration

Lumateperone 42 mg or matching placebo Capsules will be dispensed at Baseline (Week 1), and weekly thereafter until week 5 for oral administration administered once daily. Study drug will be dispensed to eligible patients under the supervision of the Investigator or Sub-Investigator, or the designated personnel authorized to administer treatment. Study drug should be taken at approximately the same time in the evening, with or without food, once daily.

[Table 2](#). provides formulation information for study drugs. Study drugs will be labeled according to local laws and regulations.

[Table 2](#).

Investigational Product	Lumateperone 42 mg	Placebo
Dose frequency	Once daily in the evening	Once daily in the evening
Route	oral	oral
Formulation	capsule	capsule
Appearance	White opaque hard gelatin capsule	White opaque hard gelatin capsule

The study drug will bear the following information:

- Protocol Number or study ID
- Statement indicating that the drug is an investigational drug
- Recommended storage conditions of drug
- Bottle number
- Lot number and date of expiration of the drug
- Quantity of drug per package

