The sponsor has requested expedited review in order to ensure funds are available for this project.

3. Is the research taking place at or using data from any of the following:

Knowing when UT's external clinical partners are involved helps inform IRB review and reporting.

- None of these
- Health Discovery Labs
- Central Health

- CommUnity Care
- Ascension locations → *Submit a request to the [Seton Site Approval Tool \(SAT\)](#) and upload the confirmation email that states the request has been submitted in UTRMS under "Other Documents." Please note, we do NOT need the final approval letter (you will not receive SAT approval until after IRB approval is granted). If you encounter issues or have questions about SAT, please reach out to [contact].*

4. Research Hypotheses

Please describe the research aims and hypotheses in the box below. Note: Procedures will be explained in a separate section below.

Aim 1: To assess the efficacy of lumateperone 42 mg administered once daily compared with placebo in the treatment of patients with Major Depressive Disorder and early life abuse, as measured by change from baseline to end of Week 6 in MADRS total score.

Aim 2: To assess neurocircuitry encoding of threat and reward learning as predictors of lumateperone response and as mechanisms of treatment action, and assess the change from pre-dose to post-dose of task-evoked brain activation.

Aim 3: MADRS response rate (proportion of subjects with an improvement $\geq 50\%$ in the Baseline MADRS total score) at Week 6 of Lumateperone as compared to Placebo.

Aim 4: MADRS remission rate (proportion of subjects with a MADRS total score ≤ 10) at Week 6 of Lumateperone as compared to Placebo.

Aim 5: To assess the efficacy of lumateperone 42 mg administered once daily compared with placebo in the treatment of patients with Major depressive Disorder and early life abuse, as measured by change from baseline to end of Week 6 in Clinical Global Impression-Severity (CGI-S) score.

5. Study Background

Provide the rationale and the scientific or scholarly background for the proposed activity, based on existing literature (or clinical knowledge). Describe the gaps in current knowledge that the project is intended to address.

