 - At Baseline (Visit 2), patients who continue to meet all eligibility criteria will be randomized to 1 of 2 treatment arms, lumateperone 42 mg or matching placebo, and will enter the 6-week DBTP. Patients will be administered the first dose of study drug in the evening of the Baseline Visit (Visit 2/Day 1). A single dose will be taken each evening, with or without food, for the duration of the 6-week DBTP.
 - MRI assessments will be completed at baseline Pre- dose and post dose at 1-week safety follow up visit.

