3.7 Prior and Concomitant Medications and Therapies

All medications taken and therapies received within 6 months prior to Screening must be noted on the eCRF. Medications taken and therapies received related to the primary indication (MDD) within the 5 years prior to Screening will also be recorded on the Concomitant medication CRF. The reported concomitant medications and/or therapies will be reviewed and evaluated by the Investigator to determine if they affect a subject's eligibility or continued participation in the study.

Medications for the acute treatment of extrapyramidal symptoms and akathisia are allowed, but should not be administered within 8 hours prior to movement disorder assessments. Zolpidem may be taken for insomnia, in the evening at bedtime and prior to midnight, but no more than 3 times per week during the Screening Period and the first 2 weeks of the DBTP only for the treatment of insomnia. Lorazepam (or other benzodiazepines) may be taken for anxiety, agitation, irritability, hostility, and restlessness. Daily doses should not exceed 3.0 mg/day during the Screening Period and through the first week of the DBTP. From Week 2 to week 6 daily dose should not exceed 2 mg/day. Doses may not be given on a standing basis, and the lowest effective dose should be used. Zolpidem or lorazepam, or their equivalents, should not administered within 8 hours prior to efficacy assessments. Any medication or therapy that is taken by or administered to the subject during the course of the study must be recorded in the ConMed CRF. The entry must include the dose, regimen, route, indication, and dates of use. All medications and other treatments taken by the subject during the study, including those treatments initiated before the start of the study, must be recorded on the ConMed CRF.

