C-SSRS	X	X	X	X	X	X	X	X
MGH-ATRQ	X							
GASS			X		X		X	X
GAD-7 QIDS-SR-16, EQ 5D-5L	X	X	X	X	X	X	X	X
PCL-5		X			X		X	X
Trauma Questionnaire	X							
CTQ	X							
EMA	X	X	X	X	X	X	X	X
Study drug dispensing		X	X	X	X	X		
Study drug compliance			X	X	X	X		
fMRI		X						X
Prior/concomitant medication								X
Adverse events								

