4.2.3 Double-blind Treatment Visits (Visits 3-7 ;Weeks 2-6)

1. Record AEs as reported by patient or observed by Investigator
2. Review concomitant medications
3. Study drug compliance check, return unused Meds at each visit
4. Vital signs (BP, pulse rate, body temperature, respiratory rate) and weight
5. Assessment Scales: MADRS, CGI-S C-SSRS, HAMD-17, GAD-7, PHQ-9, QIDS-SR-16, EQ 5D-5L and GASS
6. Lab tests for Hematology for CBC will be completed at wee4 and week6 visits and Complete BW similar to screening visit will be completed at Week-7
7. EMA Wellness App (Optional)

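### The visit and dispensing schedule puts the primary Week 6 assessment on Day 36, after about 35 doses, not after the stated six weeks of treatment

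*Protocol*

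**What the plan says.** Two sets of statements bear on treatment length.

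**Six weeks of treatment.** Under form item 7 (Study Procedure Description), "A single dose will be taken each evening, with or without food, for the duration of the 6-week DBTP", and the whole study lasts "approximately 9 weeks per subject: a 2-week screening period, 6 weeks of double-blind treatment, and a 1-week safety follow-up visit". Aim 1 defines efficacy "as measured by change from baseline to end of Week 6 in MADRS total score", and Section 11.2 repeats that time point. Form item 6 places the post-dose MRI one week after six weeks have been completed.

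**The schedule.** "Patients will be administered the first dose of study drug in the evening of the Baseline Visit (Visit 2/Day 1"). Table 1, the heading of Section 4.2.2 and Section 3.1 all label that visit Week 1. Section 4.2.3 is headed "Double-blind Treatment Visits (Visits 3-7 ;Weeks 2-6"), and Section 7.4.1 describes the post-baseline MADRS visits as weekly. Drug "will be dispensed at Baseline (Week 1), and weekly thereafter until week 5 for oral administration", which agrees with the five ticks in Table 1 ("Study drug dispensing X X X X X", Visits 2 to 6). Safety follow-up is Visit 8, Week 7.

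Sections 11.3 and 11.4 tie the primary estimand to Visit 7.

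**The concern.** If Day 1 opens Week 1 and visits are weekly, a visit labelled Week 6 comes five weeks after the first dose, not six. Treatment length is part of what the primary endpoint and the three key secondary endpoints claim to measure. Staff booking weekly visits would take the primary MADRS after five weeks, and the report would call it six.

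A site that noticed the problem might hold Visit 7 at Day 42 or 43 without supplying more drug. Section 11.2 sets to missing any MADRS taken more than 3 days after the last dose, so patients who completed treatment could lose their primary observation. With no single calendar, patients could also be booked differently from one another, which adds variation in exposure to a 50-patient trial.

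**Working it through.** **Inputs.** Visit 2 is Day 1, with the first dose that evening (form item 7). Week labels are Visit 2 = 1, Visits 3 to 7 = 2 to 6, Visit 8 = 7 (Table 1; Sections 4.2.2, 4.2.3 and 7.2.4). The interval is weekly (Sections 3.1 and 7.4.1). The window is ±2 days (Table 1). There are five dispensings (Section 3.1, Table 1). The primary visit is Visit 7 (Section 11.3).

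**The plan's own total.** 2 + 6 + 1 = 9 weeks. The sum is correct; the question is whether the schedule delivers its middle term.

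**Weekly from Day 1.** Day = 1 + 7 × (week label − 1). **Labels read as end of week.** Day = 7 × week label, with Baseline kept at Day 1.

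| Visit | Week label | Weekly from Day 1 | End of labelled week |
|---|---|---|---|
| 2 | 1 | Day 1 | Day 1 |
| 3 | 2 | Day 8 | Day 14 |
| 4 | 3 | Day 15 | Day 21 |
| 5 | 4 | Day 22 | Day 28 |
| 6 | 5 | Day 29 | Day 35 |
| 7 | 6 | Day 36 | Day 42 |
| 8 | 7 | Day 43 | Day 49 |

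**Doses before Visit 7, weekly calendar.** Day − 1 = 36 − 1 = 35. With the window, 34 − 1 = 33 to 38 − 1 = 37. Six weeks of nightly dosing is 6 × 7 = 42.
- 1 − 35/42 = 16.7% fewer
- 1 − 37/42 = 11.9% fewer
- 1 − 33/42 = 21.4% fewer

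The latest Visit 7, Day 38, is (38 − 1)/7 = 5.3 weeks after Baseline, so the window does not reach six weeks.

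**Study length, weekly calendar.** (14 + 43 − 1)/7 = 8.0 weeks. With 15-day screening and the +2-day window, (15 + 45 − 1)/7 = 8.4 weeks.

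**Does the end-of-week reading repair it?** It gives a Day 42 primary visit and a total of (14 + 49 − 1)/7 = 8.9 weeks. But Visit 3 is then 14 − 1 = 13 days after Baseline (11 to 15 with the window), against weekly visits and weekly dispensing.

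**What Week 6 means elsewhere.** The lorazepam rule in Section 3.7 sets one limit "through the first week of the DBTP. From Week 2 to week 6 daily dose should not exceed 2 mg/day". Week 1 there is the first treatment week, so Week 6 ends on Day 42.

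**A stray study day.** Section 8 places Visit 6 on Day 22 when timing a urine drug screen. Visit 6 is Day 29 or Day 35 above, so this fits neither calendar.

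**Supply, conditional.** Capsules per dispensing are not stated. If each dispensing holds exactly seven (an assumption), 5 × 7 = 35 doses and the last is on Day 35. A Day 42 or 43 visit is then 42 − 35 = 7 or 43 − 35 = 8 days later, beyond the 3-day limit. To stay within it, the last dose must be on Day 39 or 40, which takes 4 or 5 capsules more than 35.

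**The case against.** The strongest reply is a third calendar. Hold Visits 2 to 6 on Days 1, 8, 15, 22 and 29, then Visit 7 at the end of treatment Week 6 (Day 42) and Visit 8 on Day 49. Every week label matches, dispensing is weekly through Week 5, and treatment lasts about six weeks. No capsule count is given, so nothing forbids a double supply at Week 5. On this view the fault is unclear visit days, since six weeks is stated repeatedly and five weeks never.

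This does not reconcile the text. It leaves 42 − 29 = 13 days between Visits 6 and 7, although Section 7.4.1 calls the visits weekly, and it relies on a double supply that the protocol nowhere mentions. A site would have to invent both.

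Several smaller points do stand:
- The 9-week total is approximate, so 8 against 9 weeks is only supporting evidence.
- Figure 1 is not shown in the available text and the Study Day row of Table 1 may be cut. The finding therefore rests on the running text and week labels, which conflict whatever that row says.
- The off-treatment risk depends on an unstated supply. Sections 3.6 and 4.2.3 expect unused capsules to be returned, so some surplus is foreseen.
- The Day 22 reference concerns a laboratory test, not the primary endpoint.

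**Conclusion.** The concern holds and should be fixed before dosing begins. The core conflict is about 35 doses (33 to 37) against 42 at the primary visit: Day 36 where the end of Week 6 is Day 42, or Day 43 for a visit after 42 evening doses. This assumes seven-day spacing, as the text's own word weekly implies, and nightly dosing from Day 1. None of the three calendars examined fits all the text. The randomised comparison is unaffected; what would be wrong is the treatment length attached to the primary and key secondary results. Loss of primary data under the 3-day rule is possible but conditional on supply. A statistical analysis plan cannot cure this, because visit days and dispensing are protocol operations.

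**What to change.** Choose one treatment length and write it as study days.

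- **To keep six weeks:** set the primary visit at Day 43 (±2) and safety follow-up at Day 50, and supply 42 doses. The last dose is then on Day 42, and a visit as late as Day 45 is 45 − 42 = 3 days after it, still inside the on-treatment limit. The total is (14 + 49)/7 = 9 weeks. The extra week of drug can come from a sixth weekly dispensing at one added short visit, in which case visits must be renumbered and the Visit 7 references in Sections 11.3 and 11.4 updated. Alternatively, give a larger supply at an existing visit and state the longer interval openly in Sections 3.1 and 7.4.1.
- **To keep the present schedule:** restate the treatment period and all Week 6 endpoints as five weeks, and the total as eight.

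Either way, state capsules per dispensing and align Table 1, Section 3.1, the estimand definition and the Visit 6 day in Section 8. Table 1 also lacks a compliance tick at Visit 7; that is clerical, since Section 4.2.3 already requires the check.

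The cost is a short amendment to Table 1 and a few sentences. Keeping six weeks also needs one more week of drug and at most one extra short visit.
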